Participants will be randomized to one of four messaging interventions; 1) active control (CDC TIPS from former smokers campaign), 2) active control (American Lung Association campaign), 3) treatment condition including message package focused on the link between smoking and dementia, 4) no intervention control. The messaging intervention will be delivered via mail, which will include a QR code link that will allow participants to view associated motivational video. Participants will then complete the first of 2 telephone survey assessments (lasting ~30 minutes). Participants will then receive three mailers over the next couple of months and will schedule their follow-up call approximately 2.5 months later. At one to two weeks, one month, and two months after this call they will be mailed the corresponding message to their group (no intervention group will not be sent a message package). Follow up telephone assessments will occur within approximately 1-2 weeks following intervention exposure marked by date the intervention mailer was sent.

Up to 20 participants randomized to the intervention condition will complete an additional brief qualitative interview following their second telephone survey assessment (lasting ~20 minutes). The qualitative interview will focus on the perceived impact of the message, preferred number of message exposures, preferred modality of message receipt, and suggested improvement to message content. Health Believe Model (HBM) constructs assessed include: perceived severity, perceived benefits (i.e., efficacy of EBSTs; impact of quitting on ADRD risk), perceived barriers (i.e., knowledge of how to access EBSTs in healthcare setting), and self-efficacy (i.e., confidence in ability to quit in the next 30 days).

4.

Incidental or Adventitious Findings

* Will any study procedures produce incidental or adventitious findings (e.g., imaging scans, laboratory blood tests, depression screening questionnaires, etc.)?

Yes **No**

5. Instruments/Technology Involved (Includes AI/ML Algorithms)

This question is intended to identify projects involving the development or use of medical devices. This does not apply to surveys, questionnaires, or statistical analysis software.

* Are there instruments or technology of any kind, including software, tests run on samples, and algorithms, used or developed in the study?

Yes **No**

Subject Identification: Medical Records

1. Medical Record Use

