4.1. Transcriber Details

* Indicate who will perform the transcription.

Transcription will be done by a professional transcription service.

Interviews, Focus Groups, Surveys, Questionnaires

1. Tool Details

* Describe the interview tools, questionnaires, or surveys that will be used. Click the add button to provide information about each tool to be used.

View	Tool Description	Optional Qualitative Interview
	Tool Standardized	No
	File name	Outline of Qualitative Interviews_V1_2023.10.13.docx
	Tool Manner	Telephone
	Tool Manner Other	No Value Entered
	Date Modified	10/20/2023

View	Tool Description	Follow Up Survey
	Tool Standardized	No
	File name	MCAS Aim 3 3 Month Follow Up Questionnaire_V2_10_20_23_trackedchanges.docx
	Tool Manner	Telephone
	Tool Manner Other	No Value Entered
	Date Modified	10/20/2023

View	Tool Description	Baseline Survey
	Tool Standardized	No
	File name	MCAS Aim 3 Baseline Questionnaire_V5
	Tool Manner	Telephone

Tool Manner Other	No Value Entered
Date Modified	9/13/2023

2. Cognitive or Psychological Assessment

* Are any of the uploaded instruments used to assess cognitive or psychological status or function?

Yes **No**

Interviews, Focus Groups, Surveys, Questionnaires Cont.

1. Focus Group

* Will the study involve conducting focus groups?

Yes **No**

2. In-Home Visit

* Does the study involve in-home visits?

Yes **No**

Supplemental Information

1. Additional Documents

Provide any additional relevant documents (e.g., data sharing agreements, letters of support, MOUs, site permission letters), if applicable.

-  active control flyer 1(0.01)
-  active control flyer 2(0.01)
-  active control flyer 3(0.01)
-  active control videos(0.01)
-  fear flyer(0.01)
-  fear video(0.01)
-  MCAS Mailing 1 Cover Letter Active Control and Treatment Condition (Groups 1, 2, 4)_v2(0.02)
-  MCAS Mailing 1 Cover Letter No Treatment Condition (Group 3)_v2(0.02)
-  MCAS Mailing 2 Cover Letter Active Control and Treatment Condition (Groups 1, 2, 4)_v2(0.02)
-  MCAS Mailing 3 Cover Letter Active Control and Treatment Condition (Groups 1, 2, 4)_v2(0.02)
-  MCAS Mailing for Follow-up Payment v1_11_8_23.docx(0.01)
-  MCAS Video Group 1 Email 1.docx(0.01)
-  MCAS Video Group 1 Email 2.docx(0.01)
-  MCAS Video Group 1 Email 3.docx(0.01)
-  MCAS Video Group 1 Email 3_V2_10_20_23_trackedchanges.docx(0.01)
-  MCAS Video Group 2 Email 1.docx(0.01)
-  MCAS Video Group 2 Email 2.docx(0.01)
-  MCAS Video Group 2 Email 3.docx(0.01)

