1.1. Describe Documents

Describe what additional documents were added in 1.

We have added a cover letter to be included with the participants' final study payment.

Final Page

1. Assurance

- The information presented in this application is accurate;
- If the application is being submitted on behalf of the Principal Investigator (PI) rather than by the PI, the information presented was done so with the PI's agreement; and
- The specific aims and description of research (including subject population, subject interventions, collaborators, performance sites, and general scope of work) in this IRB application are consistent with those described in the sources of support listed as providing financial and/or material resources to conduct this study.

* Do you certify the above statements?

Yes No

2. Complete and Submit Application Instructions

To complete and submit this application to the IRB office, please follow the steps below:

- Select 'Finish' or 'Exit' on this page to be directed to the application workspace.
- In the application workspace, click the Submit activity to send the application to the IRB office. NOTE: The Submit activity is only available to certain study team members.

Statistical Analysis Plan

[name] will use SPSS to examine differences in changes in motivation (primary), number of 24 hour quit attempts (secondary), and use of evidence-based treatment (secondary) between groups. Specifically, she will examine differences in mean scores from baseline and follow up between the treatment group and three control groups. Given the pilot nature of this study, we will not be statistically powered to conduct regression analyses. Therefore, descriptive analyses will be the primary analytic method.

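### Do the two ways of dating the follow-up call give the no-intervention arm a different follow-up time?

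*Combined protocol and SAP*

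**What the plan says.** Research Design and Procedures, item 3 (Study Procedures and Interventions), describes one follow-up telephone survey and dates it in two ways. Participants "will schedule their follow-up call approximately 2.5 months later", which reads naturally as counted from the first survey call. The paragraph then says: "Follow up telephone assessments will occur within approximately 1-2 weeks following intervention exposure marked by date the intervention mailer was sent".

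The mailing schedule lies between these two statements: "At one to two weeks, one month, and two months after this call they will be mailed the corresponding message to their group". It carries an exception for one arm: "no intervention group will not be sent a message package".

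The file list in Supplemental Information, item 1, is consistent with that exception. The no-treatment condition has one listed letter, "MCAS Mailing 1 Cover Letter No Treatment Condition (Group 3)_v2(0.02". The later letters are for the other three groups only, for example "MCAS Mailing 3 Cover Letter Active Control and Treatment Condition (Groups 1, 2, 4)_v2(0.02". The no-intervention arm is fourth in the procedures and Group 3 in the file names, which is a labelling difference.

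The Statistical Analysis Plan makes change in motivation primary. It adds "number of 24 hour quit attempts (secondary), and use of evidence-based treatment (secondary) between groups", compares the treatment group with three control groups, and states: "Therefore, descriptive analyses will be the primary analytic method". It gives no visit window and no adjustment for length of follow-up.

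**The concern.** A four-arm comparison needs the same clock in every arm. Here one of the two dating rules refers to a single mailer when three are planned, and it cannot be applied to an arm that is sent no message. The documents do not say which rule takes priority.

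The two secondary outcomes can build up with time. If the three message arms were called by the mailing rule and the no-intervention arm by the 2.5-month rule, the no-intervention arm would have longer to report quit attempts or treatment use. A descriptive analysis without adjustment would carry that difference into the comparison, where it could pass for a weaker effect of the messages. If a reader took the mailing rule to mean the first mailer, the mismatch would be weeks rather than days.

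**Working it through.** **Inputs.** From the study procedures: mailers at 7–14 days, one month and two months after the first call; follow-up 7–14 days after the mailer, or at 2.5 months. From Subject Population, item 1: 220 participants. Assumptions: one month = 30.4 days; equal allocation, so 220/4 = 55 per arm; Poisson counts; a constant attempt rate of 0.5 to 1.0 per person over 76 days; no true effect of the messages.

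**Step 1: which mailer fits?** The 2.5-month date is 2.5 × 30.4 = day 76.0.

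| Mailer | Sent (day) | Call = sent + 7 to 14 | Days before day 76 |
|---|---|---|---|
| First | 7–14 | 14–28 | 48–62 |
| Second | 30.4 | 37.4–44.4 | 31.6–38.6 |
| Third | 60.8 | 67.8–74.8 | 1.2–8.2 |

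Dating from the first or second mailer puts the call before the third mailer goes out on day 60.8. That contradicts both the three-mailer schedule and the 2.5-month statement. The third is the only reading that agrees with the rest of the paragraph.

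**Step 2: does the no-intervention arm have a date?** Yes. The 2.5-month statement is made for participants generally, and the exception for this arm removes the message package, not the call. The Statistical Analysis Plan also needs a follow-up score from this arm, since it compares treatment with all three control groups.

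**Step 3: worst mismatch.** Suppose message arms are called by the third mailer and the no-intervention arm at day 76. The ratio of windows is 76/74.8 = 1.016 to 76/67.8 = 1.121, so the no-intervention window is 2% to 12% longer. Expected counts in the message arms are 74.8/76 = 0.984 to 67.8/76 = 0.892 of those in the no-intervention arm.

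**Step 4: in standard errors.** With rate λ and window ratio r, the difference is λ(1 − r) and SE = √[(λ + λr)/55].

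| λ | Call, days after third mailer | r | Difference | SE | Difference/SE |
|---|---|---|---|---|---|
| 0.5 | 14 | 0.984 | 0.008 | 0.134 | 0.06 |
| 0.5 | 10.5 | 0.938 | 0.031 | 0.133 | 0.23 |
| 0.5 | 7 | 0.892 | 0.054 | 0.131 | 0.41 |
| 1.0 | 14 | 0.984 | 0.016 | 0.190 | 0.08 |
| 1.0 | 10.5 | 0.938 | 0.062 | 0.188 | 0.33 |
| 1.0 | 7 | 0.892 | 0.108 | 0.185 | 0.58 |

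The top value needs every message-arm call at exactly 7 days, every no-intervention call at exactly day 76, and the higher rate.

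**Step 5: direction.** Under the mailing rule a late third mailer delays the message-arm call by the same number of days. A delay of more than 1.2 to 8.2 days moves that call past day 76 and reverses the sign.

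**The case for a change.** The strongest case for a change is that the ambiguity is real and cheap to remove. Naming the third mailer would still leave the no-intervention arm without a date under the mailing rule. One date counted from the baseline call would cover all four arms with no extra contacts. Because the analysis is descriptive and unadjusted, equal follow-up has to come from the design. The follow-up questionnaire's file title calls it a three-month instrument (3 × 30.4 = about day 91), which is another label that does not match.

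The textual points stand: two statements, an unnamed mailer, and no mailing date for one arm. The consequence does not follow from them. Nothing in the plan tells staff to use different rules by arm, and both statements are given as approximate, so a gap of 1 to 8 days is largely within their own tolerance. Counting only from baseline would also drop the lag from last exposure to assessment, which the plan sets deliberately. Calling the no-intervention arm on the date matching the third mailing would give equal timing and keep that lag, so the choice is partly preference. The questionnaire title is a file name that applies to every arm and creates no difference between them.

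**Conclusion.** The concern does not call for a change. The paragraph is loosely worded, but its parts fit together on one reading: the call comes about 2.5 months after the first call, shortly after the third mailer, in all arms. Staff who follow that reading give near-equal follow-up, and the descriptive conclusions are sound.

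Even if the two rules were split by arm, the mismatch is 1 to 8 days and the shift 0.06 to 0.58 of a standard error, about 0.23 to 0.33 at the middle of the one-to-two-week range. It would affect two secondary outcomes, only against the no-intervention arm. Treatment and the two active controls share the same mailing rule, and no effect on motivation, the primary outcome, has been shown. The direction is uncertain because late mailings would reverse it. If the questionnaire, which is not shown, asks about a fixed recent period, the effect on counts largely disappears.

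These figures rest on equal allocation, Poisson counts and the assumed attempt rates. The conclusion also rests on 2.5 months being counted from the first call, which is the natural reading but not an explicit one.

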* Will medical records be used to identify subjects or records?

Yes **No**

Risks and Benefits

1. Direct Benefits Intended

For this type of research there are generally no direct benefits to subjects. The response to this question, "There are no direct benefits to subjects", would be acceptable.

* Are any of the research activities intended to directly benefit subjects?

Yes No

2. Potential Benefits to Society

Describe how the research might help future patients.

* Describe the importance of the knowledge reasonably to be gained from this study and what benefit the research may provide to society.

The knowledge gained from this study will identify the most impactful motivational message to promote smoking cessation and the use of evidence-based cessation treatment in older adult smokers. This population of smokers are particularly at risk for all of the known health effects of smoking, including dementia.

3. Direct Physical Intervention

A physical intervention refers to study procedures that may pose a risk (however minimal) to a subject's body (e.g., blood draws, MRI scans, drug or device trials, exercise, dietary restrictions/supplements). Examples of activities that are NOT physical intervention include obtaining informed consent and administering surveys.

* Does this study involve direct physical intervention with subjects?

Yes No

4. Potential Psychosocial Risks

For this type of research the risks to subjects are generally limited to the risk of breach of confidentiality. The response to this question, "There is a risk of breach of confidentiality", would be acceptable.

* Describe any potential psychosocial risks to subjects, such as psychological stress or confidentiality risks (including risk to reputation,

economic risks, and legal risks).

There is a risk of a confidentiality breach.

Participants may become upset or experience discomfort.

5. Procedures to Minimize Risks

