The response to this question should address how the risk of breach of confidentiality will be minimized. For example, it could be described that the study team has several measures in place to protect against a breach of confidentiality, such as limiting the number of people who view identifiable information, coding study instruments, storing study data in restricted areas and on computers that are password-protected, only transmitting coded data outside the institution (if data will be shared), and using a secure web-interface to transmit data off-site (if data will be shared).

* Describe the procedures in place to minimize risks from all interventions performed for research purposes. This should include activities in place to identify, monitor, mitigate, and eliminate risks to the degree possible.

Data will be stored securely according to campus policy.

Participants will be informed of the approximate length of study activities during the consent process and will be offered the opportunity to take breaks during the study activities if needed.

Participants will be informed about all aspects of the study during consent and have the option to skip or withdraw from any activities that make them upset or uncomfortable.

Subject Population

1. Total Subjects

You must provide an integer. If you are enrolling a range of subjects (e.g., 50 to 100 subjects), enter the larger number.

* Provide the number of subjects that will be enrolled at sites for which UW Madison is serving as the reviewing IRB.

220

2. Inclusion Criteria

* Describe the main inclusion criteria.

- Adults between the ages of 50-80
- Self-reported current smoker
- Do not hold a current diagnosis of dementia or Mild Cognitive Impairment (MCI)
- Can read/write in English

3. Exclusion Criteria

* Describe the main exclusion criteria.

History of Mild Cognitive Impairment (MCI) or dementia.

4. Targeted Populations

Populations could be racial/ethnic, sex, or gender (this also applies to gender identity, or lack thereof).

* Will this study target or exclude specific populations?

Yes No

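### Upset or discomfort is a named risk, but the plan describes no systematic recording of it in any arm, so it cannot be compared between arms

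*Combined protocol and SAP*

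**What the plan says.** - **The risk.** Risks and Benefits, item 4 (Potential Psychosocial Risks) names two risks. One is a confidentiality breach. The other is: "Participants may become upset or experience discomfort".
- **The protections.** Item 5 (Procedures to Minimize Risks) tells the applicant what the answer must cover: "This should include activities in place to identify, monitor, mitigate, and eliminate risks to the degree possible". For upset, the answer says that participants "will be offered the opportunity to take breaks during the study activities if needed", and that they will be informed at consent and "have the option to skip or withdraw from any activities that make them upset or uncomfortable". Consent Overview, item 1 adds that consent covers how to reach study staff and that an information sheet is mailed after the first call.
- **The exposure.** Research Design and Procedures, item 3 sends the message by post with a QR code to a video: "At one to two weeks, one month, and two months after this call they will be mailed the corresponding message to their group". Two telephone surveys are planned, the second about 2.5 months after the first.
- **What is measured.** The same item says that Health Belief Model "constructs assessed include: perceived severity, perceived benefits", and goes on to barriers and self-efficacy. In the section on interviews and questionnaires, the form asks: "Are any of the uploaded instruments used to assess cognitive or psychological status or function". The answer marked is No.
- **What is analysed.** The SAP lists "differences in changes in motivation (primary), number of 24 hour quit attempts (secondary), and use of evidence-based treatment (secondary) between groups", with descriptive analysis as the main method.
- **The interview.** Up to 20 people in the intervention condition are asked about the message's impact, the number of exposures, the mode of delivery and possible improvements.

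**The concern.** The study tests a dementia-risk message with a view to wider use. The background section describes dementia as what older adults fear most about ageing, and the uploaded materials include a flyer and a video with fear in their file names. That these files belong to the treatment arm is an inference. People read or watch the material away from staff.

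The form asks for steps that identify and monitor risk. The steps listed reduce risk, but none of them finds out whether anyone was upset. Followed as written, the study could report that one message motivates more than another without being able to say whether it also upset more people. These data cannot be recovered after the follow-up calls are done. Some participants who leave because they were upset, and do not say so, would look the same as any other missed follow-up.

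**Working it through.** The plan gives no distress rate, sample-size calculation or allocation ratio, so there is no stated figure to reproduce. The check has three parts.

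**1. Is upset recorded anywhere in the visible plan?**

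| Place | Could it show upset? | All arms? |
|---|---|---|
| Survey constructs (severity, benefits, barriers, self-efficacy) | Not listed | n/a |
| Instrument declaration on psychological status | Answered No | n/a |
| SAP outcomes (motivation, quit attempts, treatment use) | Not listed | n/a |
| Skip, withdraw or contact staff | Only if the participant acts; no log by arm described | Yes |
| Optional interview | Perhaps, through the question on impact | No: at most 20, treatment arm only |

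No row gives a planned, uniform record in all four arms.

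**2. How long from the first mailing to the next planned survey call?**

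- Follow-up call: 2.5 × 30.4 = 76 days after the first call.
- First mailing: 7 to 14 days after the first call.
- Gap: 76 − 14 = 62 days to 76 − 7 = 69 days, about 9 to 10 weeks, with two more mailings inside it.

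The protocol also places follow-up 1–2 weeks after exposure. With only two surveys planned, this fits the last mailing (2.5 − 2 = 0.5 months, about 15 days) and does not imply extra calls.

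**3. What would one item asked of everyone give?**

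Assumptions: equal allocation, 220/4 = 55 per arm, and full follow-up. All distress rates below are assumed. A second column uses 44 per arm (an assumed 20% loss: 55 × 0.8).

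Upper limit with zero reports: two-sided 95% is 1 − 0.025^(1/n); one-sided 95% is 1 − 0.05^(1/n).

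| | n = 55 | n = 44 | n = 20 (interview only) |
|---|---|---|---|
| Two-sided upper limit | 6.5% | 8.0% | 16.8% |
| One-sided upper limit | 5.3% | 6.6% | 13.9% |

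Chance of at least one report, 1 − (1 − p)^n:

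| True rate p | n = 55 | n = 20 |
|---|---|---|
| 1% | 42% | 18% |
| 2% | 67% | 33% |
| 5% | 94% | 64% |
| 10% | 99.7% | 88% |

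Half-width of the 95% interval for a difference between two arms with the same rate p, 1.96 × √(2p(1 − p)/55). This is a normal approximation and is rough at low rates:

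- p = 5%: 8.1 points
- p = 10%: 11.2 points
- p = 20%: 15.0 points

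Power at two-sided 5% with 55 per arm is 41% for 5% against 15%, 67% for 5% against 20%, and 85% for 5% against 25%.

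The interview would cover at most 20/55 = 36% of the treatment arm and nobody in the other three, so it supports no comparison.

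**The case against.** The other side has several good points.

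- **The protections are not confined to calls.** A reader might infer that they are, because breaks suit a live interview. The option to skip or withdraw covers any activity, so it reaches an unopened flyer or an unwatched video. Participants also receive an information sheet after the first call, and consent covers how to contact staff. Video emails are listed as well and may offer a way to reply. This stands. These routes reduce risk, but they do not ask about upset.
- **The questionnaires are not shown.** The No concerns psychological status or function, and a single item on reaction to a message could exist without changing that answer. The list of constructs need not be complete. This also stands, so the point is limited to what the documents describe.
- **Upset would not necessarily go undetected.** Stated withdrawals, unprompted contacts and the interview could each reveal cases. What is missing is a systematic record.
- **Upset is not shown to be the main harm, or to come from the mailings.** Two risks are named without ranking or attribution, and the breaks fit discomfort in a 30-minute survey equally well. The waiver section calls the intervention benign and of minimal risk. Nothing here is evidence of harm. But that classification does not supply data on a risk that the plan itself names.
- **The numbers are small.** They are, and a late item does not shorten the 9–10 week gap or reach people lost before follow-up. The SAP is descriptive in any case, and at present no estimate is planned.

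**Conclusion.** The point holds as a gap in ascertainment and reporting. The visible documents name upset as a risk, describe no uniform way of recording it in any arm, and include no such outcome in the SAP. Distress from the mailed messages may therefore be missed, and it cannot be compared between arms. The motivation, quit-attempt and treatment-use results are not themselves invalidated.

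With one common item, zero reports in an arm would put the two-sided upper limit at about 6.5% (5.3% one-sided). This assumes 55 per arm and complete follow-up; with 44 per arm it would be 8.0%. Only large between-arm differences would show. The conclusion also rests on the unseen questionnaires containing no such item.

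**What to change.** 1. The sponsor first confirms whether the baseline or follow-up questionnaire already asks about upset. If it does, adding that item to the SAP may be enough, provided that it is worded alike in all arms.
2. If not, add one fixed item to the existing follow-up telephone survey: whether anything the participant has read, seen or heard about smoking and health since the first call upset them, with a severity rating. Use the same words in all four arms, without reference to a mailing, so that the no-intervention arm can answer. Ask it after the outcome items so that it cannot affect them.
3. Log by arm every withdrawal or contact that cites upset.
4. In the SAP, report the count and percentage by arm with exact two-sided 95% intervals beside the primary result, labelled descriptive.

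The cost is under a minute of call time and a minor IRB change. The item may prompt some reports, as it would in every arm. People lost before follow-up are covered only by the log. The text of the mailing cover letters is not shown and may already give a contact or withdrawal line, so no change to them is proposed.
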